7.0 EFFICACY EVALUATION

The FAS was used for the summary of the efficacy endpoints. All the efficacy data are presented in Appendix 16.2.6.2 and 16.2.6.3.

7.1 Primary and Secondary Efficacy Endpoint

The median percentage of days with neither daytime nor nighttime heartburn for subjects in the dexlansoprazole capsules group (51.72%) was greater than for subjects in the placebo group (32.67%) with the difference of 19.05%. The difference between treatment groups was not statistically significant ($P=0.057$) (Table 7.a).

Subgroup analyses were performed on the primary endpoint, and these results are presented in Table 7.b. For subjects with positive *H pylori* results, the median percentage of days with neither daytime nor nighttime heartburn for subjects in the dexlansoprazole capsules group (68.62%) was greater than for those in the placebo group (34.62%), and the difference (34.00%) was statistically significant with $p\text{-value} = 0.032$. For subjects with the highest overall study drug compliance ($\geq 90\%$), the median in the dexlansoprazole capsules group (51.72%) was also greater than for those in the placebo group (30.29%), and the difference (21.43%) was statistically significant with $p\text{-value} = 0.037$.

For the secondary endpoint of percentage of days without nighttime heartburn over 4 weeks, the median value of dexlansoprazole capsules group (67.86%) was greater compared with placebo group (54.67%). The difference (13.19%) between treatment groups was not statistically significant ($P=0.268$) (Table 7.a).

For the percentage of days without daytime heartburn over 4 weeks, the median value of dexlansoprazole capsules group (62.96%) was greater compared with placebo group (46.55%) (Table 7.a).

An ad hoc sensitivity analysis was performed on the primary and secondary efficacy endpoints.. For primary efficacy endpoint, the difference between treatment groups was statistically significant ($P=0.029$) (Table 15.2.6). For the secondary efficacy endpoint, the difference between the treatment groups was not statistically significant ($P=0.365$) (Table 15.2.7).

Table 7.a Percentage of Days Without Heartburn During Treatment (Full Analysis Set)

	Placebo QD N = 108	Dexlansoprazole 30 mg QD N = 107
Primary endpoint: percentage of days with neither daytime nor nighttime heartburn during treatment ^a		
N	108	107
Mean (SD)	36.98 (31.999)	47.21 (35.995)
Median	32.67	51.72
P-value ^b		0.057
Secondary endpoint: percentage of days without nighttime heartburn during treatment		
N	108	107
Mean (SD)	50.38 (34.309)	54.83 (37.449)
Median	54.67	67.86
P-value ^b		0.268
Additional endpoint: percentage of days without daytime heartburn during treatment		
N	108	107
Median	46.55	62.96

Source: [Table 15.2.1](#).

QD: once daily.

^a Percentage of days with neither daytime nor nighttime heartburn = (the days that are heartburn-free during treatment period) / (total number of days for which either a daytime or nighttime result is marked during treatment period) × 100%.

^b The 2-sided p-value was obtained using the Wilcoxon rank-sum test.

Table 7.b Subgroup Analyses of Percentage of Days With Neither Daytime Nor Nighttime Heartburn Over 4 Weeks (Full Analysis Set)

	Placebo QD N=108	Dexlansoprazole 30 mg QD N=107
Age (<45 years)		
N	46	50
Mean (SD)	39.40 (34.297)	53.09 (34.458)
P-value		0.068
Age (≥45 to 65 years)		
N	57	53
Mean (SD)	35.02 (29.633)	41.79 (36.018)
P-value		0.472
Age (≥65 years)		
N	5	4
Mean (SD)	37.17 (41.722)	45.37 (52.932)
P-value		0.898
Gender (Male)		
N	43	47
Mean (SD)	34.40 (33.307)	49.51 (37.033)
P-value		0.063
Gender (Female)		
N	65	60
Mean (SD)	38.70 (31.248)	45.40 (35.370)
P-value		0.381
BMI (<25 kg/m²)		
N	69	72
Mean (SD)	37.94 (31.249)	45.50 (36.638)
p-value		0.298
BMI (≥25 to 30 kg/m²)		
N	34	28
Mean (SD)	34.93 (33.229)	51.55 (36.338)
p-value		0.104
BMI (≥30 kg/m²)		
N	5	7
Mean (SD)	37.78 (40.352)	47.39 (30.665)
p-value		0.744

	Placebo QD N=108	Dexlansoprazole 30 mg QD N=107
H pylori status (positive)		
N	41	40
Mean (SD)	39.87 (30.941)	55.95 (35.893)
p-value		0.032
H pylori status (negative)		
N	67	67
Mean (SD)	35.22 (32.733)	41.99 (35.294)
p-value		0.403
Overall study drug compliance (<80%)		
N	0	1
Mean (SD)		0.00 (NA)
p-value		NA
Overall study drug compliance (80-<90%)		
N	1	3
Mean (SD)	83.33 (NA)	64.74 (37.701)
p-value		>0.999
Overall study drug compliance (≥90%)		
N	106	103
Mean (SD)	35.95 (31.370)	47.15 (35.884)
p-value		0.037

Source: Table 15.2.2.

Note 1: Percentage of days with neither daytime nor nighttime heartburn = (the days that are heartburn-free during Treatment Period)/(Total number of days for which either a daytime or nighttime result is marked during Treatment Period) * 100%.

Note 2: The p-value was obtained using the Wilcoxon rank-sum test.

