5.10.1 Primary Efficacy Endpoint

The percentage of days with neither daytime nor nighttime heartburn over the 4 weeks of treatment was summarized descriptively. Comparisons between dexlansoprazole capsules and placebo was made using a Wilcoxon rank-sum test. The two-sided p-value was presented for the difference between dexlansoprazole capsules and placebo; the difference was considered statistically significant if the p-value was less than 0.05.

The percentage of days with neither daytime nor nighttime heartburn was calculated for each subject who has at least 1 daytime or nighttime heartburn result (presence or absence of heartburn) during the 4 weeks of treatment (up to last dose day or Day 35 whichever is first) by calculating:

$$\text{Percentage of days with neither daytime nor nighttime heartburn} = \frac{\text{(the days that were heartburn-free during Treatment Period)}}{\text{(Total number of days for which either a daytime or nighttime result was marked during Treatment Period)}} \times 100\%;$$

all entries on a day must be heartburn-free in order for the day to be counted as a day with neither daytime nor nighttime heartburn.

The days with missing diary results for both daytime and nighttime were excluded from the numerator and denominator. If a subject prematurely terminated, the Treatment Period was defined as from first dose date to last dose date + 1 day. If last dose date was missing, then 35 days was imputed as treatment period.

Subgroup Analyses:

Similar descriptive statistics and Wilcoxon rank-sum tests were repeated on the primary endpoint to evaluate the treatment effect within the different baseline subpopulation levels as follows:

- Age (<45, ≥45 to <65, ≥65 years).
- Gender (male, female).
- BMI (<25, 25-<30, ≥30 kg/m²).
- *H pylori* status (positive, negative).
- Overall study drug compliance (<80%, 80-<90%, ≥90%).

Ad Hoc Sensitivity Analysis

Similar descriptive statistics and two sample T-test were repeated on the primary endpoint to evaluate the treatment effect.

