7.3 Efficacy Conclusions

In this 4-week study comparing treatment with dexlansoprazole 30 mg QD or placebo in Chinese subjects with symptomatic nonerosive GERD, subjects treated with dexlansoprazole had a greater percentage of days with neither daytime nor nighttime heartburn and without nighttime heartburn than subjects taking placebo, but these differences were not statistically significant according to the pre-planned analysis.

Subjects in the dexlansoprazole treatment group with positive *H pylori* results or who were $\geq 90\%$ compliant with study drug did have a statistically significantly greater percentage of days without daytime and nighttime heartburn than those in the placebo group. Subjects in the dexlansoprazole treatment group also had statistically significantly greater reduction in severity of heartburn, acid regurgitation, and belching according to investigator assessment of symptoms after 4 weeks of treatment. In addition, subjects taking dexlansoprazole had a statistically

significantly greater percentage of days without rescue medication use over 4 weeks of treatment.

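### The H. pylori-positive result (p=0.032) is reported as statistically significant from unadjusted within-level tests after the primary test failed, with no interaction estimate and without its H. pylori-negative counterpart in the text

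*SAP*

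**What the plan says.** The document supplied as the SAP is a past-tense analysis report. Its section 5.10.1 sets the criterion for the primary comparison: "the difference was considered statistically significant if the p-value was less than 0.05". Under Subgroup Analyses it states that similar descriptive statistics and "Wilcoxon rank-sum tests were repeated on the primary endpoint to evaluate the treatment effect within the different baseline subpopulation levels". Five factors are listed: age, gender, BMI, H. pylori status and overall study drug compliance. No interaction test is described, and no adjustment for the number of tests. The efficacy analysis section of the protocol (13.1.3) describes no subgroup analysis.

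Section 7.1 reports the overall primary result as not significant (p=0.057). It then picks out two subgroup levels. For H. pylori-positive subjects it gives medians of 68.62% and 34.62%, "and the difference (34.00%) was statistically significant", p=0.032. The other level is compliance of at least 90% (p=0.037). The H. pylori-negative result, p=0.403, is in Table 7.b and is not mentioned in the text. Section 7.3 first says that the overall differences were not significant under the pre-planned analysis. It then says that dexlansoprazole subjects in the two selected levels "did have a statistically significantly greater percentage of days without daytime and nighttime heartburn than those in the placebo group".

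**The concern.** A p-value below 0.05 in one level and above it in the other says little about whether treatment works differently in the two. The levels differ in size and in sampling error, and the direct comparison is the interaction. Here no interaction is given, and the text shows only the level that crossed 0.05.

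The error rate is also uncontrolled. The primary test did not reject, so nothing in the plan passes a 5% error rate down to the subgroup tests, and many levels are tested. Calling one of them statistically significant in the efficacy conclusions gives it a standing that the design does not support. A reader of 7.1 and 7.3 alone could take it that efficacy has been shown in H. pylori-positive patients.

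**Working it through.** **Inputs.** Table 7.b, as n, mean (SD):
- H. pylori-positive: placebo 41, 39.87 (30.941); dexlansoprazole 40, 55.95 (35.893).
- H. pylori-negative: placebo 67, 35.22 (32.733); dexlansoprazole 67, 41.99 (35.294).

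**1. Can the inputs be trusted?** The Wilcoxon p of 0.032 needs subject-level data and cannot be recomputed. The summaries can be checked in three ways.
- Overall t-test from Table 7.a: p=0.0287 (report: 0.029).
- Weighted H. pylori means: placebo (41×39.87 + 67×35.22)/108 = 36.99; dexlansoprazole (40×55.95 + 67×41.99)/107 = 47.21. Table 7.a gives 36.98 and 47.21.
- A t-test in the positive level gives p=0.034, close to the reported 0.032. In the negative level it gives 0.25, against a reported Wilcoxon p of 0.403.

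**2. Effects by level.**
- Positive: 55.95 - 39.87 = 16.08, SE = sqrt(30.941²/41 + 35.893²/40) = 7.45.
- Negative: 41.99 - 35.22 = 6.77, SE = sqrt(32.733²/67 + 35.294²/67) = 5.88.

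The 34.00-point figure in 7.1 is a difference of medians (68.62 - 34.62). The mean difference in the same subjects is about half of that.

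**3. Interaction on the mean scale.**
- Difference between effects: 16.08 - 6.77 = 9.31.
- SE = sqrt(7.45² + 5.88²) = 9.49.
- z = 9.31/9.49 = 0.98, p = 0.33.
- 95% CI = 9.31 ± 1.96×9.49 = -9.3 to 27.9.
- With pooled variance (F on 1 and 211 df): p = 0.33, CI -9.5 to 28.1.

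**4. Does the scale matter?** The planned test is rank-based, so two approximations were made from the reported Wilcoxon p-values.
- Mann-Whitney index, with null SE = sqrt((n1+n2+1)/(12·n1·n2)): 0.638 (SE 0.065) against 0.542 (SE 0.050). z = 1.18, p about 0.24.
- SEs implied by the p-values: 16.08/2.144 = 7.50 and 6.77/0.836 = 8.10; combined 11.03. p about 0.40.

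**5. Power of the interaction test.** If the true difference were 9.31 with SE 9.49, two-sided power at 0.05 is P(Z > 1.96 - 0.98) + P(Z < -1.96 - 0.98), about 17%.

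**6. Chance of a level below 0.05 under no effect.** Table 7.b has 12 numeric p-values. Ten belong to the baseline factors (age 3, gender 2, BMI 3, H. pylori 2) and two to compliance. Simulating no treatment effect with rank-sum tests at the Table 7.b arm sizes, and assuming the four baseline factors unrelated to one another, gives at least one baseline level below 0.05 in about 30% of trials.

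**7. The other baseline factors.** The same mean-scale calculation gives interaction p-values of about 0.38 for gender, 0.76 for age and 0.69 for BMI.

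**The case against.** Four replies deserve weight.

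*H. pylori status is a listed subgroup factor.* It is, and the choice of factor is not at issue. Listing a factor does not make an unadjusted p-value confirmatory once the primary test has failed.

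*The report never says that the effect differs by H. pylori status.* That is correct. A reader might infer effect modification because only the positive level is discussed, but neither 7.1 nor 7.3 asserts it, and the negative result is shown in Table 7.b. The fault is selective wording without an interaction estimate, not a false statement about interaction.

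*The interaction test is weak.* This stands. With about 17% power, p=0.33 cannot be read as showing equal effects, and the interval allows a difference of nearly 28 points.

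*The claim does not travel far.* This also stands. Section 7.3 puts the failed primary result first, and H. pylori is absent from the discussion (9.1), the conclusion (9.2) and the synopsis conclusion.

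On multiplicity, a reader might treat the 12 p-values as independent and compute 1 - 0.95^12 = 46%. That overstates the risk. The factors partition the same 215 subjects. The compliance level of at least 90% holds 209 of them (106 + 103), so it nearly repeats the overall test. The 80 to below 90% level has 1 and 3 subjects and cannot reach 0.05 by an exact rank-sum test.

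**Conclusion.** The concern holds as a fault of inference and reporting. The H. pylori-positive result is one of ten unadjusted baseline-level tests after a primary p of 0.057. Its effect does not differ detectably from that in H. pylori-negative subjects: difference 9.3 points, 95% CI -9.3 to 27.9, p about 0.33, with other approximations between about 0.24 and 0.40. A procedure of this kind would produce at least one baseline level below 0.05 in about 30% of trials with no treatment effect.

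The interaction figures rest on normal theory applied to published summaries. The 30% rests on the baseline factors being unrelated to one another. The documents support neither the conclusion that H. pylori status is irrelevant to the effect nor the conclusion that the report's overall finding depends on this subgroup. No primary or overall conclusion changes. The correction should be made, but it is confined to 7.1 and 7.3.

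**What to change.** The tests have been run and the report is complete, so section 5.10.1 should continue to describe them as performed.
- Label all within-level p-values in 5.10.1, 7.1, 7.3 and Table 7.b as exploratory and unadjusted for multiplicity.
- Add a treatment-by-subgroup interaction estimate with 95% CI for age, gender, BMI and H. pylori status. State the model and scale, and identify it as added after unblinding.
- Give the mean difference with 95% CI for every level in Table 7.b.
- In 7.1 and 7.3, report both H. pylori levels together and remove the description of the positive level as statistically significant.

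The cost is four interaction analyses on existing data, extra columns in one table, and the loss of one favourable statement. The primary analysis is untouched.

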5.9 Study Drug Exposure and Overdose

Overall study drug compliance (%) was determined as (total count of capsules taken / total number of days on study drug) \times 100%. The total number of days on study drug (exposure) was

calculated as date of last dose of study drug - date of first dose of study drug + 1, assuming no gaps in the dosing interval. Any gaps in dosing interval was ignored in the calculation of the total. If last dose date was missing, then 35 days were imputed as treatment period. Summary statistics for the total number of days on study drug and overall compliance were generated for the safety analysis set.

The number and percentage of subjects with overall study drug compliance of <80%, 80-<90%, and ≥90% was also summarized for the safety analysis set. Subjects with unreturned study drug were assumed to have taken 1 capsule of study drug for each day of exposure for the calculation of overall compliance. Subjects with overall compliance ≥100% were set to 100% in the analysis.

In addition, diary compliance was determined as the percentage of days during treatment with two diary entries:

$$\text{Diary Compliance} = \frac{\text{(Number of days with two diary entries collected during treatment period)}}{\text{(Number of days with two diary entries expected during treatment period)}} \times 100\%$$

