6.3 Analysis Sets

A total of 217 subjects were randomized and included in the randomized set: 109 subjects in placebo group and 108 subjects in the dexlansoprazole capsules group. Two subjects were excluded from the safety analysis set and full analysis set because they did not receive study drug (Table 15.1.7). The remaining 215 subjects were included in the safety analysis set and full analysis set: 108 subjects in placebo group and 107 subjects in dexlansoprazole capsules group.

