The results of Study TAK-390MR_302 showed that, although subjects in the dexlansoprazole group had a greater percentage of days with neither daytime nor nighttime heartburn than those taking placebo, the results of the primary endpoint (percentage of days and nights without heartburn) did not reach statistical significance based on the original planned analysis ($p=0.057$). Statistical significance was missed by a small margin. As an indication of how close the results were to reaching significance, when analyzed in subjects with the highest treatment compliance ($\geq 90\%$), the difference was statistically significant; these results indicate that dexlansoprazole treatment was more effective than placebo for treating Chinese subjects with symptomatic nonerosive GERD when the medication was taken consistently. Subjects who took dexlansoprazole also had a greater percentage of nights without heartburn than those who took placebo, but the difference was not statistically significant. Subjects in the dexlansoprazole group had statistically significantly greater reductions in investigator-assessed symptoms of heartburn, acid regurgitation, and belching after 4 weeks of treatment, and also used statistically significantly less rescue medication than subjects in the placebo group.

After the unblinded results for the primary and secondary endpoints were available, an *ad hoc* sensitivity analysis (two sample t-test) was performed to explore the influence of the higher than expected placebo response in light of the fact that the p-value for the primary analysis of the primary endpoint was insignificant by only a small amount. The sensitivity analysis results in a statistically significant difference between the group means for the primary endpoint (percentage of days with neither daytime nor nighttime heartburn, $p=0.029$). The difference between groups

for the secondary endpoint (percentage of days without nighttime heartburn) was not statistically significant based on the sensitivity analysis ($p=0.365$).

The results of Study TAK-390MR_302 were similar to Study T-GD05-137 (on which the assumptions for study power were based) for measuring the dexlansoprazole treatment effect, but were not consistent for measuring the placebo effect. Because this was a well-controlled clinical trial, a few of the reasons that might explain this outcome are discussed herein.

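### Table 7.b: one placebo subject with about 100% heartburn-free days is in no study-drug compliance level; if that subject belongs at 90% or above, p = 0.037 becomes borderline

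*SAP*

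**What the plan says.** SAP Section 6.3 puts "108 subjects in placebo group and 107 subjects in dexlansoprazole capsules group" in both the safety set and the full analysis set (FAS). Section 5.10.1 lists overall study drug compliance (below 80%, 80 to below 90%, 90% or more) among the subgroup factors for the primary endpoint, and sets the criterion that "the difference was considered statistically significant if the p-value was less than 0.05".

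Section 5.9 defines compliance as capsules taken divided by days on drug. It fills two gaps. A missing last dose date gives 35 days of treatment. For missing returns, "Subjects with unreturned study drug were assumed to have taken 1 capsule of study drug for each day of exposure". The three categories are to be summarised for the safety set. Section 5.2.2 says that, dates apart, missing data were not imputed.

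The compliance block of Table 7.b prints:

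- from the row beginning "Overall study drug compliance (<80": placebo N = 0; dexlansoprazole N = 1, mean 0.00
- 80 to below 90%: placebo N = 1, mean 83.33; dexlansoprazole N = 3, mean 64.74 (SD 37.701)
- from the row beginning "Overall study drug compliance (≥90": placebo N = 106, mean 35.95 (31.370); dexlansoprazole N = 103, mean 47.15 (35.884); p = 0.037

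The table's two notes define the endpoint and say that "The p-value was obtained using the Wilcoxon rank-sum test". Sections 7.1 and 7.3 call the 90%-or-more result statistically significant. Section 9.1 cites the result "when analyzed in subjects with the highest treatment compliance" as an indication that the drug outperformed placebo when taken consistently.

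**The concern.** The placebo compliance levels are one subject short of the analysis set named in the table title, and neither table note mentions it. A one-off typing error in an N would be trivial. A real subject left out is not, because each subgroup p-value depends on who is in the row. Here the omitted value sits at the ceiling of the scale in the placebo arm, so its absence can only help the active arm. The affected p-value lies just under 0.05, in a trial whose primary test gave 0.057, and the Discussion uses it as support for efficacy. This is a question of reconciling the table with its own analysis set. It is separate from whether compliance, which is measured after randomisation, makes a sound subgroup.

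**Working it through.** **1. Reproduce Table 7.a from the other factors.** Pool the levels of each factor in Table 7.b: the mean is Σnm/Σn, and the SD comes from the within-level plus between-level sums of squares. The target for placebo is N = 108, 36.98 (31.999).

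- Age (46 + 57 + 5): N = 108, 36.985 (31.999)
- Sex (43 + 65): N = 108, 36.988 (31.999)
- BMI (69 + 34 + 5): N = 108, 36.985 (31.999)
- *H pylori* (41 + 67): N = 108, 36.985 (31.999)
- Compliance (0 + 1 + 106): N = 107, 36.39 (31.556), which does not match

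Dexlansoprazole compliance (1 + 3 + 103) gives N = 107, 47.20 (35.995), against 47.21 (35.995) in Table 7.a, so that arm is complete. The placebo mean and SD fail together with the N. An observation is absent; the count is not merely misprinted.

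**2. Solve for the absent value.**

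- From the means: 108 × 36.98 − 106 × 35.95 − 83.33 = 3993.84 − 3810.70 − 83.33 = 99.81. Rounding of the printed means allows 98.7 up to the ceiling of 100.
- From the SDs, with sum of squares = (n − 1)SD² + n·mean²: placebo FAS 257,253.4; 90%-or-more level 240,322.7; the single 80 to below 90% subject 83.33² = 6,943.9. The remainder is 9,986.7 (unrounded sums), and √9,986.7 = 99.9.
- Adding exactly 100 to the 107 returns 36.98 (31.999), the Table 7.a figures.
- The endpoint uses at most 35 diary days, so the next possible value below 100 is 34/35 = 97.1%, outside the rounding range.

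The subject therefore counts in the primary analysis, with about 100% heartburn-free days, but in no compliance level.

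**3. Effect if the subject belongs at 90% or above.**

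- Placebo mean: (106 × 35.95 + 100)/107 = 36.55. The mean difference goes from 47.15 − 35.95 = 11.20 to 47.15 − 36.55 = 10.60.
- Rank-sum statistic: p = 0.037 gives z = 2.086. With n = 106 and 103, SD(U) = √(106 × 103 × 210/12) = 437.1, so U exceeds its null mean by 2.086 × 437.1 ≈ 912.
- A placebo value at 100 lowers this excess by 103/2 − T/2, where T is the number of dexlansoprazole subjects in the level also at 100%. The new SD(U) is √(107 × 103 × 211/12) = 440.2.
- T = 0: (911.7 − 51.5)/440.2 = 1.954, p = 0.0507
- T = 5: p = 0.0500
- T = 10: p = 0.0494
- T = 15: p = 0.0487

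Varying T from 0 to 15, a tie factor on the variance from 0.95 to 1, and the rounding of 0.037 (0.0365 to 0.0375) gives 0.048 to 0.052. As a cross-check, 1,453 simulated data sets approximately matched the printed means, SDs and medians and had a starting p near 0.037. Adding one placebo value at 100 gave a mean p of 0.0496 (95% range 0.0465 to 0.0528).

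**4. Effect otherwise.** If the subject belongs in a lower level, the 90%-or-more row is unchanged, and the placebo N of 0 (below 80%) or 1 (80 to below 90%) should be one higher. If compliance cannot be derived, the row is also unchanged, but the table needs a missing category.

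**The case against.** The strongest reply is that the documents show an unexplained omission, not a broken rule. Section 5.9 covers a missing last dose date and unreturned drug. It does not cover drug that was returned but never usably counted, and under Section 5.2.2 such a count would stay missing. A reader might infer that 5.9 gives every treated subject a value and that dropping this one breached it. The text does not say so, and this part of the reply stands.

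The level is also unknown. The unreturned-drug rule would give 100% compliance, but the 35-day rule can place a subject lower: 28 capsules over 35 imputed days is 80%. Section 9.1's statement that at least 97% of 215 subjects exceeded 90% compliance does not settle it, since 209/215 = 97.2% and 210/215 = 97.7% both fit.

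A reader might also infer that the result loses significance once the subject is restored. That is too strong: the restored p falls on either side of 0.05, crossing at about five tied dexlansoprazole subjects, and the number of ties is not printed.

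Finally, the explanation may lie in the source tables, the listings or the separate file note cited in Section 11.0. That is possible, but a reader of Table 7.b still needs to be told. The primary result, the synopsis and the formal conclusion in Section 9.2 do not use this subgroup, which limits the severity.

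**Conclusion.** The point holds as a reconciliation failure with a possible effect on one reported p-value. It is certain from the printed figures that the placebo compliance levels are one subject short and that this subject had about 100% heartburn-free days. The change from 0.037 to about 0.048 to 0.052 is conditional: it assumes the subject belongs at 90% or above, that the printed 0.037 is correct for the 209 subjects shown, and a normal approximation with an unknown number of ties. The documents support calling the restored result borderline. They do not support saying that significance is lost, that the SAP rule was breached, or that the 90%-or-more row is necessarily wrong. The primary analysis (N = 108, p = 0.057) includes the subject and does not change. This is a should-fix, because Sections 7.1, 7.3 and 9.1 rely on the affected p-value.

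**What to change.** Trace the placebo subject, apply the Section 5.9 rules, and re-issue Table 7.b and its source Table 15.2.2 with placebo compliance levels that total 108. If the subject falls at 90% or above, update that row's N, mean, SD and p-value, and the median and difference quoted in Section 7.1. If the subject falls lower, correct that level's N and summary statistics. If compliance cannot be derived, print a missing row with the reason, and report a sensitivity p-value with the subject placed at 90% or above. Then bring the statements of statistical significance in Sections 7.1, 7.3 and 9.1 into line with the rerun.

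The cost is one data query, one table rerun and a few sentences. The price to the sponsor is that a favourable subgroup p-value may become borderline or pass 0.05.
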